5.2 Methods of minimising bias

Not placebo-controlled: We intend to use a control-group to compare effects. Unfortunately, a placebo-controlled study design is not possible in this case: a placebo would have to be approximately equisweet without any known metabolic effects. However, there are no such substances: artificial sweeteners such as e.g. aspartame are much sweeter and it would be impossible to keep the blinding. Apart from that, artificial sweeteners probably have metabolic side-effects and are not inert. All carbohydrates have some metabolic effects themselves. We accept the possible placebo-effect of the two polyols. However, participants will serve as their own controls (before-after treatment) as well.

Possible confounders: We accept that a possible confounder might be the substitution of sucrose in daily life as polyols might serve as a substitute. If sugar consumption is reduced, metabolic effects could be caused by reduced sugar exposure rather than polyol intake. We will therefore assess overall sugar consumption before and during the trial. Participants will keep a food diary.

Steps to reduce loss to follow up: We will call the volunteers once a week in order to achieve maximal compliance and minimize loss to follow-up.

5.2.1 Randomisation

The principal investigator [name] [name] prepares a treatment list and enrolled participants are consecutively entered into this list. The treatment list is prepared beforehand by a (excel) computer-based randomization.

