5.2.2 Blinding procedures

- The personnel performing analyses of faecal, urine and blood samples is blinded concerning the treatment group the participants belong to (control, xylitol, or erythritol).
- Control group: the study nurse, principal investigator and study participant are *not* blinded.
- Patients receiving either polyol are blinded as to which substance is used (xylitol or erythritol). The principal investigator and the study nurse are *not* blinded.

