5.3 Unblinding Procedures (Code break)

Unblinding is permissible in case of an adverse event which results in premature study termination. The principal investigator is in possession of the key and will inform the participant in this case.

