6.2 Recruitment and screening

Participant recruitment will be achieved through referring physicians from the Ernährungszentrum St. Claraspital, where morbidly obese patients are seen in an outpatient clinic before bariatric surgery and are usually on a rather long waiting list before surgery. In case patients are interested in participating, they will be contacted by the principal investigator (Dr: [name]) or the study nurse ([name]) per email, phone or face-to-face and a pre-screening is carried out (key questions to find out whether a volunteer is eligible). If the volunteer meets these key criteria, a screening appointment will be made and informed consent is sent by email or mail, so that the volunteer gets the chance to read through the information material before the screening visit.

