6.3 Assignment to study groups

The principal investigator [name] [name] prepares a treatment list and enrolled participants are consecutively entered into this list. The treatment list is prepared beforehand by a (excel) computer-based randomization and cannot be changed.

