8.3.2 Second Visit = 1. Metabolic Visit

The **second visit (1. metabolic visit)** at our outpatient clinic will take about 2.5 hours. We will carry out an oral glucose tolerance test and take blood, and urine samples. If possible, the participant will bring the first faecal sample to this visit. Again, the participant has to arrive on an empty stomach (not allowed to eat or drink 10 hours prior to this appointment except for tap water or unsweetened herbal tea without milk). Even chewing gum must be avoided, as they might contain sugar. In addition 2 days prior to the test the participant has to refrain from heavy physical activity and needs to have carbohydrates as part of her/his meals.

- The candidate will be assigned randomly to one of the three groups (intake of xylitol, or erythritol or control group).
- The participant needs to bring his/her study folder along, including the food diary which he/she should have kept over the course of 1 week.
- If possible, the participant will bring along the first faecal sample
- We will take a first blood sample to measure blood sugar, insulin, C-peptide (for the oral glucose tolerance test). In addition we will measure biomarkers of inflammatory response (IL-6, TNF- α, sTNFR1, sTNFR2) and intestinal permeability (zonulin and LPS).
- The participant will receive 75 g of glucose (grape sugar) plus 3g 3-O-Methyl-D-glucose dissolved in 300mL tap water which he/she will have to drink over a period of 5-10min. ("oral glucose tolerance test")
- After 30, 60, 90 and 120min we will again take blood samples for measurement of blood sugar, insulin, C-peptide and 3-OMG. In total we will take a maximum of 30mL blood (corresponding to 3 tablespoons).
- During this appointment we will fill in the questionnaire for gastrointestinal symptoms together with the participant.
- At the end of the visit, the participant will receive the portioned sweeteners (if assigned to one of the polyol groups) and the kit for the second faecal sample.

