10.4.2 Primary Analysis

Descriptive statistics will be used for demographic variables, such as age, weight, height and BMI. Hormone and glucose profiles will be analyzed by calculating the area under the concentration-time curve (AUC) from baseline values. The parameters will be tested for normality by the Shapiro-Wilk test method. One-way ANOVA will be applied to describe differences between the groups. Student's paired t-test will be used to test for significant differences between subjects before and after sweetener intake. All statistical analysis will be done using the statistical software package, SPSS for Windows, Version 22.0 (SPSS Inc., Chicago, USA). Values will be reported as mean \pm SEM. Differences will be considered to be significant when P < 0.05. Statistics will be done by the principal investigator with support of Prof. [name], biostatistician.

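### Allocation is not concealed: the unblinded principal investigator makes and holds the advance list and shares recruitment, and nothing requires baseline measures to be complete before the arm is revealed

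*Protocol*

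**What the plan says.** **Allocation.** Protocol 5.2.1 states that the principal investigator "prepares a treatment list and enrolled participants are consecutively entered into this list". Section 6.3 repeats this and adds: "The treatment list is prepared beforehand by a (excel) computer-based randomization and cannot be changed". Section 5.3 says of the code: "The principal investigator is in possession of the key and will inform the participant in this case".

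**Blinding.** For the polyol arms, 5.2.2 states: "The principal investigator and the study nurse are *not* blinded". The same holds in the control arm, where the participant is unblinded too. Participants on a polyol do not know which one they receive. The staff who analyse faecal, urine and blood samples are blinded to group.

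**Recruitment.** Section 6.2: "In case patients are interested in participating, they will be contacted by the principal investigator" or by the study nurse, and a pre-screening follows. Section 5.1 describes the same arrangement.

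**Analysis.** Section 10.4.2: "Statistics will be done by the principal investigator with support of" a biostatistician. Section 10.4.1 compares post-treatment values of the sweetener groups with control, and 10.4.2 names one-way ANOVA between groups and paired t-tests within participants.

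**Order at V2.** The first bullet of 8.3.2 reads: "The candidate will be assigned randomly to one of the three groups (intake of xylitol, or erythritol or control group". The fasting sample and OGTT come in later bullets, followed by: "During this appointment we will fill in the questionnaire for gastrointestinal symptoms together with the participant". Sweetener is handed out at the end of the visit. Section 8.3.3 requires the baseline measures before intake begins. Both copies of the Schedule of Assessments mark randomisation at V2 but the baseline GSRS at the screening visit (V1).

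**The concern.** Randomisation protects against selection only if whoever enters participants cannot foresee the next assignment. Here the list exists in advance, is filled in order of enrolment, and is made by someone who also contacts and pre-screens candidates. That person could know the next arm while eligibility and the date of entry are still open.

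A rule against changing the list stops editing. It does not stop anyone choosing whom to enter next, or when. No independent holder, central service or envelope system appears in 5.2, the section on minimising bias, or in 6.3.

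A second gap concerns timing. If the arm is revealed before the V2 baseline measures, those measures are no longer certain to be pre-allocation values. This matters most for a subjective symptom score completed with unblinded staff, by a participant who would know whether he or she is a control.

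At stake is the comparison with the no-sweetener group, which is open to participants and staff and is judged at P < 0.05. Section 10.2 says that the findings will serve to plan larger studies.

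**Working it through.** The protocol gives no power, SD or design figure to reproduce. The check is a comparison of sections, followed by an illustration on stated assumptions.

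**Step 1: is the next arm foreseeable?**
- List made in advance and fixed: 5.2.1, 6.3.
- Filled consecutively: 5.2.1, 6.3.
- Made by the principal investigator, who holds the key: 5.2.1, 5.3.
- The principal investigator takes part in recruitment: 5.1, 6.2.
- Concealment step: none described.

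Together these make the next assignment knowable to at least one recruiter. Under concealed simple 1:1:1 allocation, a guess would be right about one time in three.

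**Step 2: do other provisions cover it?**
- Blinded laboratory staff (5.2.2) protect the measurement of glucose, insulin and C-peptide. They have no influence on who enters which arm.
- The between-group analysis (10.4.1, 10.4.2) states no baseline adjustment, so a selected imbalance would pass into the post-treatment contrast.
- Non-compliant participants are excluded (6.4, 7.4), and drop-outs are replaced in a per-protocol analysis (10.4.1). If replacements come from the same list, their entry is exposed in the same way.

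**Step 3: order of assignment and baseline.**
- 8.3.2 lists assignment before the OGTT and GSRS, but gives no disclosure time and does not say that its bullets are in time order.
- 8.3.3 places the baseline measures before intake, not before allocation is revealed.
- Baseline GSRS: V1 in the schedule, V2 in 8.3.2. Both cannot be the plan.

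**Step 4: illustration.** The number steered and the 1 SD difference are assumptions; neither is in the protocol. Let k of the 20 participants in a sweetener arm, and k of the 20 in control, be steered in opposite directions, each differing by 1 SD on a characteristic that persists to the post-treatment value.
- Shift per arm = (k/20) × 1 SD. Shift in the contrast = 2 × k/20 = 0.10k SD.
- Standard error of a difference between two arms of 20 = √(1/20 + 1/20) = √0.10 = 0.316 SD.

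| k per arm | Shift in contrast | Shift ÷ standard error |
|---|---|---|
| 1 | 0.10 SD | 0.32 |
| 2 | 0.20 SD | 0.63 |
| 3 | 0.30 SD | 0.95 |

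A stable difference between participants is present both before and after treatment, so it cancels in the paired before-after tests. The illustration applies to the post-treatment comparison with control.

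**The case against.** **This is an exploratory pilot with blinded assays and paired tests.** The blinding of laboratory staff is a real safeguard and limits assay bias in the primary outcome. The paired tests remove stable differences between participants. Neither protects the comparison with control from selection at entry.

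**The principal investigator does not act alone.** Recruitment is shared with the study nurse and the statistics have biostatistician support. But the nurse is unblinded too, and support in the analysis does not conceal the list.

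**Section 10.4.1 compares baselines across groups.** With 20 per arm, a difference reaches P < 0.05 only at about twice the standard error, 2 × 0.316 = 0.63 SD. The illustrated shifts lie well below that and would usually pass unnoticed.

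**A reader might infer that allocation is disclosed at the start of V2, before the baseline OGTT and GSRS.** The documents do not establish this. It rests on bullet order alone. The folder, diary and faecal sample that participants bring with them are also listed after assignment, and the only fixed point for hand-out is the end of the visit. The GSRS may fall at V1, before randomisation. What stands is that the order is not fixed.

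**Nor are all baselines exposed.** Lipids, liver enzymes, hsCRP and leucocytes are taken at V1. The food diary covers the week before V2, and the first faecal sample is collected at home and brought to V2 if possible. The exposed baselines are mainly the OGTT samples, the V2 serum and urine, and the GSRS if it is done at V2. No sweetener has been taken by then.

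**Conclusion.** The concealment defect holds on the protocol's own text. The plan describes allocation and, followed as written, leaves the next arm knowable to someone who recruits. This is more than a missing detail, and it should be corrected.

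The timing point holds in a narrower form: assignment is listed first at V2, nothing requires the baseline measures to be complete before the arm is revealed, and the visit for the baseline GSRS is contradictory.

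The size cannot be derived from the document. The range of 0.10 to 0.30 SD against a standard error of 0.32 SD rests wholly on the assumed 1 to 3 steered participants per arm and a 1 SD difference. It shows that a few selective entries could shift the contrast by up to about one standard error. It does not show that any steering occurs or is intended.

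A reader might go further and object that the principal investigator's part in the statistics makes the analysis itself invalid. The document does not support that: a biostatistician is involved, and analysis on coded arms is commonly left to a statistical analysis plan, which is not shown here.

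**What to change.** **Sections 5.2.1 and 6.3.** Have the biostatistician already involved under 10.4.2, who has no recruiting role in the protocol, generate the list and supply assignments in sequentially numbered, opaque, sealed envelopes. If blocks are used, vary the block sizes and keep them undisclosed, because unblinded staff who know a fixed block size can predict its last assignments. State that the principal investigator and study nurse have no access to upcoming assignments.

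**Section 5.3.** Align the wording so that the principal investigator learns a participant's arm only after it has been assigned. The code-break role can then stay as it is for participants already allocated.

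**Section 8.3.2.** State that the envelope is opened only after eligibility is confirmed and the last OGTT sample, the urine sample and any V2 GSRS are complete, immediately before sweetener hand-out.

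**Section 8.3.2 and both copies of the Schedule of Assessments.** Reconcile the visit at which the baseline GSRS is taken.

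**Cost.** Wording, envelopes and a short task for someone already on the team. The one practical burden is that the list must be kept outside the recruiting team.

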5.2.2 Blinding procedures

- The personnel performing analyses of faecal, urine and blood samples is blinded concerning the treatment group the participants belong to (control, xylitol, or erythritol).
- Control group: the study nurse, principal investigator and study participant are *not* blinded.
- Patients receiving either polyol are blinded as to which substance is used (xylitol or erythritol). The principal investigator and the study nurse are *not* blinded.

5.3 Unblinding Procedures (Code break)

Unblinding is permissible in case of an adverse event which results in premature study termination. The principal investigator is in possession of the key and will inform the participant in this case.

6. STUDY POPULATION

6.1 Eligibility criteria

Participants fulfilling all of the following inclusion criteria are eligible for the study:

- Obese volunteers (BMI > 30kg/m2) aged 18- max. 55 years
- Otherwise healthy.
- Informed Consent as documented by signature (Appendix Informed Consent Form)

The presence of any one of the following exclusion criteria will lead to exclusion of the participant:

- Known cardiovascular disease (coronary heart disease, cardiopathy, arrhythmia, pace-maker)
- Diabetes mellitus treated by oral antidiabetics or insulin
- Arterial hypertension with antihypertensive treatment
- Dyslipidaemia with statin therapy
- Known chronic hepatic disease (NASH, hepatitis). NAFLD is no exclusion criterion
- Known renal disease: kidnev failure
- Pregnancy: although no contraindication for polyol intake, pregnancy might influence metabolic state and vascular function
- Women who are pregnant, Intention to become pregnant during the course of the study,
- Lack of safe contraception, defined as: Female participants of childbearing potential, not using
 and not willing to continue using a medically reliable method of contraception for the entire study
 duration, such as oral, injectable, or implantable contraceptives, or intrauterine contraceptive

- devices, or who are not using any other method considered sufficiently reliable by the investigator in individual cases
- Chronical diseases of the gastrointestinal tract (also irritable bowel disease, food intolerance), history of gastrointestinal surgery with major changes to the gastrointestinal tract (removal of stomach, larger portions of the small bowel/colon, any bypass).
- Intake of prebiotics (such as inulin, oligofructose) on a regular basis
- Intake of probiotics (e.g. capsules with live bacteria or yeasts) on a regular basis
- Intake of pro/prebiotic food on a regular basis (e.g. Activia, Actimel, Aktifit, Yacult etc). Intake of common yoghurt is allowed, but limited to 1 serving/day
- Substance abuse, alcohol abuse
- Inability to follow procedures due to psychological disorders, dementia or insufficient
- Knowledge of project language (German).
- Participation in another study with investigational drug within the 30 days preceding and during the present study.

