11.2 Data management	29
11.2.1 Data Management System	29
11.2.2 Data security, access and back-up	30
11.2.3 Analysis and archiving	30
11.2.4 Electronic and central data validation	30
11.3 Monitoring	30
11.4 Audits and Inspections	30
11.5 Confidentiality, Data Protection	30
11.6 Storage of biological material and related health data	30
12. PUBLICATION AND DISSEMINATION POLICY	30
12.1 Funding	30
13. INSURANCE	30
14. REFERENCES	31
15. APPENDICES	32

STUDY SYNOPSIS

	Abteilung für Forschung				
Sponsor	St. Claraspital Basel				
Principal Investigator	nvestigator [name] [name] Abteilung für Forschung St. Claraspital Basel [name]				
	[contact]				
	Email: [contact]				
Study Title:	Effect of the natural sweeteners erythritol and xylitol on gut microbiota and glucose tolerance in obese volunteers: A pilot study				
Short Title / Study ID:	n/a				
Protocol Version and Date:	Version 2, 6.6.2016, Version 3, 25.9.2017				
Trial registration:	Clinical Trial Gov				
Study category and Rationale	A: Study without drugs, without medical devices with low risk: life-style intervention study using food additives (E967 and E968).				
(=007 1500)					
Objective(s):	but obese cohort. Effect of daily intake of xylitol or erythritol over 7 weeks on gut microbiota and glucose tolerance				

	Primary endpoint: 1) Glycaemic control (fasting insulin & glucose & c-peptide after oral glucose challenge)
	Secondary endpoints:
	2) Human gut microbiota composition 3) Metabolomics
Outcome(s):	4) Blood lipid profile and hepatic enzymes
	5) Inflammatory response
	6) Intestinal permeability
	7) Gastrointestinal tolerance (bloating, diarrhoea etc.)
	8) intestinal glucose absorption
Ct. d. danima	This pilot trial is a randomized, controlled interventional study; the project set-up will be
Study design:	single-centre, national.
Inclusion / Exclusion	Inclusion criteria:
criteria:	- Obese volunteers (BMI > 30kg/m2)
oritoria.	- Aged 18- max. 55 years
	- Otherwise healthy.
	Exclusion criteria:
	- Known cardiovascular disease
	- Diabetes mellitus treated by oral antidiabetics or insulin
	- Arterial hypertension with antihypertensive treatment
	- Dyslipidaemia with statin therapy - Known chronic hepatic disease (NASH, hepatitis).
	- Known chronic nepatic disease (NASH, nepatitis) Known renal disease: kidney failure
	- Pregnancy
	- Intake of proton pump inhibitors (PPIs) on a regular basis

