	- Intake of proton pump inhibitors (F Pis) on a regular basis - Intake of antibiotics within the last 3 months before inclusion
	- Intake of pro or prebiotics
	- Chronical diseases of the gastrointestinal tract, history of gastrointestinal surgery with
	major changes to the gastrointestinal tract - Substance abuse, alcohol abuse.
	- Substance abuse, accord abuse Inability to follow procedures due to psychological disorders, dementia or insufficient
	knowledge of project language (German).
	Over a period of 7 weeks, volunteers will ingest the natural sweetener xylitol or erythritol
Measurements and	(or no additional sweetener). Once before and after these 7 weeks we will carry out an
procedures:	oral glucose tolerance test, examine faeces and urine (gut microbiota and metabolomics)
	and take blood samples to analyse lipid profile and liver enzymes. Volunteers will fill in
	a food diary and a questionnaire for gastrointestinal symptoms. The whole study will take
	approximately 8 weeks.
Otrode Due doot /	Randomization to the three study arms will be done by a computer based randomization
Study Product /	(excel). The control group will not receive any sweetener.
Intervention:	The two intervention groups will receive either xylitol or erythritol as follows:
	1st week = run-in (adaption week)
	- 2 days 1 *portion per day (1-0-0)
	- 3 days 2 portions per day (1-1-0)
	- 2 days 3 portions /day (1-1-1)
	2nd to 7th week: Over four weeks the volunteers will ingest 3 portions/day.
	*1 portion xylitol = 8g, 1 portion erythritol = 12g
Control Intervention	We will compare
	a) Baseline findings to post treatment findings. In this way each volunteer will serve as
	his/her own control.
	b) A control group will show whether findings are stable within a participant over 7 weeks.
Number of	In total will enrol 60 volunteers, of which 20 will be controls, 20 will be treated with xylitol
Participants with	and 20 erythritol. This is a pilot trial and a power analysis is not possible. However, we
Rationale:	assume that a relevant difference between the treatments should be observed in 20
-	subjects in each group.
Study Duration:	We plan to carry out this trial within approximately 1 year, starting in August 2016 till
	October 2018, depending on recruitment.
Study Schedule:	Month Year of First-Participant-In (planned): 1st August, 2016
Investigates/a	Month Year of Last-Participant-Out (planned): 1st October, 2018
Investigator(s):	[name] [name]

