Background and Rationale:	Bei krankhaft Übergewichtigen (Body Mass Index über 35kg/m2) kommt es zu zahlreichen Folgeerkrankungen wie metabolem Syndrom, Bluthochdruck und Vorstufen von Diabetes. Xylit und Erythrit werden seit den 1970er Jahren vor allem in der Zahnhygiene eingesetzt, da sich gezeigt hat, dass diese Substanzen die Zusammensetzung der Speichelbakterien günstig beeinflusst (Kariesreduktion). Xylit scheint zudem auch positive Effekte auf den Stoffwechsel zu haben, insbesondere auf die Zuckerverwertung, die bei Übergewichtigen oft gestört ist auch wenn keine Zuckerkrankheit vorliegt. Im Tierversuch zeigt sich, dass Xylit die insulinproduzierenden Inselzellen in der Bauchspeicheldrüse anregt, zu einer Reduktion des Bauchfettes führt und die Zuckerverwertung verbessert. Bei künstlichen Süssungsmitteln wie Aspartam und Acesulfam-K konnte in einer Studie gezeigt werden, dass die Darmbakterienzusammensetzung sich verändert und es zu einer Störung der Zuckerverwertung kommt. Über die Auswirkung von Xylit und Erythrit auf die Darmbakterien ist bisher noch nichts bekannt. Mit dieser Studie möchten wir diese Effekte bei einem nicht-diabetischen, aber übergewichtigen Kollektiv (BMI ab 30kg/m2) prüfen.

Objective(s):	Wir möchten untersuchen, ob Erythrit- und Xyliteinnahme als Süssungsmittel einen Effekt auf die Darmbakterienzusammensetzung und die Zuckerverwertung hat
Outcome(s):	Primärer Endpunkt: - Effekte auf die Zuckerverwertung (oraler Glukosetoleranztest)
	Sekundäre Endpunkte:
	- Effekte auf die Zusammensetzung der Darmbakterien
	- Effekte auf den Stoffwechsel (Metabolomics)
	- Effekte auf die Darmpermeabilität
	- Effekte auf den Entzündungszustand
 	- Effekte auf die intestinale Glukoseabsorption
Study design:	Interventionell-experimentelle, randomisierte, Parallelstudie
Inclusion / Exclusion criteria:	In diese Studie sollen insgesamt 60 adipöse Probanden (BMI ≥ 30kg/m2), Frauen und Männer (Alter: 18-55 Jahre), eingeschlossen werden. Allgemein gute körperliche Verfassung, kein Diabetes mellitus, keine arterielle Hypertonie, keine vorgängige Operation wie Magenbypass, keine Erkrankungen des Magendarmtraktes. Keine Antibiotikatherapie in den letzten 3 Monaten vor Studienbeginn.

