3. STUDY OBJECTIVES

Overall Objective

The purpose of this study is to evaluate whether daily intake of erythritol or xylitol over a period of 7 weeks will alter gut microbiota composition and glucose tolerance.

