6.4 Criteria for withdrawal / discontinuation of participants

Participants might have to be excluded, in case of:

- Non-compliance
- Intolerable gastrointestinal effects (diarrhoea)
- Need for systemic antibiotic therapy
- Any other non-foreseeable adverse events

In case of discontinuation, already collected biological and health-related data will be used for analysis, except if the person concerned wishes to be excluded from analysis altogether. Encryption will be maintained at all times.

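### The exclusion list in section 6.1 leaves out two exclusions set in the synopsis: regular PPI use and antibiotics in the three months before inclusion

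*Protocol*

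**What the plan says.** The Study Synopsis, under inclusion and exclusion criteria, bars people with "Intake of proton pump inhibitors (PPIs) on a regular basis" and with "Intake of antibiotics within the last 3 months before inclusion". The summary in German repeats the second item: "Keine Antibiotikatherapie in den letzten 3 Monaten vor Studienbeginn". It does not mention PPIs.

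Section 6.1 is the full eligibility section. It begins "Participants fulfilling all of the following inclusion criteria are eligible for the study" and then states that the presence of any single listed exclusion keeps a person out. Its list names neither PPIs nor prior antibiotics. The items closest to the microbiota are prebiotics, probiotics and pro/prebiotic foods, for example "Intake of probiotics (e.g. capsules with live bacteria or yeasts) on a regular basis". Ordinary yoghurt is limited to one serving a day.

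For antibiotics taken during the study, section 6.4 says "Participants might have to be excluded, in case of" and includes "Need for systemic antibiotic therapy" in the list that follows. Section 7.6 asks that antibiotic use be reported and gives as its reason a possible effect on vascular assessment.

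**The concern.** The synopsis and section 6.1 define different populations, and a site cannot follow both. The two missing items are not remote from the trial's purpose. The overall objective in section 3 is to find out whether the sweeteners "will alter gut microbiota composition and glucose tolerance", and section 10.1 offers favourable microbiota change as a possible explanation for any glycaemic benefit.

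Section 10.4.1 relies heavily on before-after comparison, with each participant as his or her own control. If a person finishes a course of antibiotics shortly before the baseline stool sample, any recovery over the next seven weeks is recorded as change. In a sweetener arm it would look like an effect of the sweetener. In the control arm it would disturb the stability over time that this arm is meant to show.

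**Working it through.** There is no stated figure to reproduce. The check is a comparison of the two lists.

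**Exclusions in the synopsis (13), and whether section 6.1 has them**

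| Synopsis item | In 6.1? |
|---|---|
| Cardiovascular disease | yes |
| Drug-treated diabetes | yes |
| Treated hypertension | yes |
| Statin-treated dyslipidaemia | yes |
| Chronic hepatic disease | yes |
| Renal disease | yes |
| Pregnancy | yes |
| Regular PPI intake | **no** |
| Antibiotics in the prior 3 months | **no** |
| Pro- or prebiotics | yes, but now limited to regular intake |
| Gastrointestinal disease or surgery | yes |
| Substance or alcohol abuse | yes |
| Inability to follow procedures | yes |

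Count: 13 − 2 = 11 carried over, 2 missing. Section 6.1 also adds items of its own: contraception, intention to become pregnant, and participation in another study. It is thus the longer and more detailed list, and a reader would expect it to contain everything in the synopsis.

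**Deliberate change or oversight?** Three points favour oversight.
1. Section 6.1 expands the neighbouring pro/prebiotic item into three lines. Restricting yoghurt while admitting someone just off antibiotics would make little sense.
2. Section 6.4 treats antibiotic need during the study as a possible ground for removal, so the investigators regard antibiotics as relevant.
3. Sections 6.1 and 7.6 refer to vascular function or vascular assessment, and the running page title names vascular function, although section 4 has no vascular outcome. This suggests text carried over from a related study.

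**Could another criterion cover the gap?** The requirement to be otherwise healthy does not: a healthy volunteer may have taken antibiotics last month.

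**Which comparison is affected?**
- Within-participant change (section 10.4.1): recovery after antibiotics enters directly as change.
- Comparison with control: randomisation spreads such people over the arms on average, so the effect is mainly added noise, plus chance imbalance in small arms. One participant is 1/20 = 5% of an arm.
- PPIs: the protocol gives no mechanism. Steady use at both visits would largely cancel within a person. The point here is only that the synopsis meant to keep these people out.

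**The case against.** The synopsis and section 6.1 belong to one protocol, and the antibiotic exclusion is stated twice in it. A reader might infer that section 6.1 overrides the synopsis and that recent antibiotic users are plainly eligible. The documents do not support that: nothing says which text prevails, so eligibility is ambiguous rather than clearly widened. Section 6.2 also describes a pre-screening with key questions, and the pre-screening and screening forms listed in section 15 are not shown. They may carry both items. This stands, and it limits the finding to a contradiction in the text. It does not remove the need to correct section 6.1, because a form that carried both items would then disagree with that section.

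It is also fair to say that microbiota composition is a secondary outcome in an exploratory pilot, and that the control arm and randomisation blunt the effect on between-arm comparisons. Both are true, and they are why no bias size is claimed.

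A second stronger reading is tempting. The wording "Participants might have to be excluded, in case of" leaves removal for antibiotics during the study open, the principal investigator and study nurse know the arm (section 5.2.2), and analysis is per protocol with replacement (section 10.4.1). A reader might infer that this biases the analysed set by arm. The documents do not show it. Section 6.4 does address antibiotics, discretion over withdrawal is ordinary, nothing suggests a motive related to arm, and membership of the per-protocol set may be settled in an analysis plan that is not at hand. What remains is a minor gap in wording: non-compliance (section 7.4) and poor tolerance (section 7.3) have a fixed consequence, and antibiotics do not.

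**Conclusion.** The contradiction is certain: two of the 13 synopsis exclusions are missing from section 6.1, and no redaction or gap in the text explains it. It should be corrected, because it decides who is enrolled and bears on an outcome in the overall objective.

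The size of any effect cannot be derived. It depends on how many recent antibiotic users or regular PPI users would present, which the documents do not say, and on what the screening forms contain. The harm described for antibiotics assumes that the microbiota is still recovering at the baseline sample; the sponsor's own three-month window implies that view. The documents do not show that any ineligible person was enrolled.

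**What to change.** Add the two synopsis lines, unchanged, to the exclusion list in section 6.1, and make sure the pre-screening and screening forms carry both. The wording already exists. The cost is two lines, possibly a few more screen failures, and submission to the ethics committee, since section 1.15 names changes to eligibility criteria among those that need an amendment.

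Two minor changes are at the sponsor's choice and could go in the same amendment. In section 6.4, replace the open wording for systemic antibiotics during the study with one rule applied identically in all three arms; which rule is for the sponsor to decide. Mandatory withdrawal would be simple but loses the final visit, because sections 7.5 and 8.2.5 plan none after discontinuation. In section 7.6, replace the reference to vascular assessment with the microbiota and glycaemic endpoints.
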